13.3 Secondary Analyses

Secondary efficacy variables will be summarized using continuous descriptive statistics (n, mean, SD, median, minimum, and maximum) by visit and treatment group. Two-sample t-tests will be used to analyze the efficacy variables for visit-based data between treatment groups.

Change from baseline in secondary efficacy variables will be summarized by visit and treatment group using continuous descriptive statistics. Change from baseline will be analyzed using an ANCOVA model adjusting for baseline value and site, and with treatment group as the explanatory variable. Two-sample t-tests will be used for sensitivity analysis. Paired t-tests will be used to assess change from baseline within each treatment group.

All secondary efficacy analyses will be performed on the ITT population with control-based multiple pattern mixture model imputation. All secondary endpoints will be described under subject listings.

The following secondary efficacy variables will be tested:

- Fluorescein staining by region: central, superior, inferior, temporal, nasal, and corneal sum as assessed by the Ora Calibra® Corneal and Conjunctival Staining Scale;

- Lissamine green staining by region: central, superior, inferior, temporal, nasal, and conjunctival sum as assessed by the Ora Calibra® Corneal and Conjunctival Staining Scale
- Conjunctival Redness as assessed by the Ora Calibra® Scale
- TFBUT
- Tear Osmolarity
- Unanesthetized Schirmer's Test
- Blink Rate
- Ora Calibra® Ocular Discomfort Scale
- Ora Calibra® Ocular Discomfort & 4-Symptom Questionnaire
- Visual Analog Scale: Burning/Stinging, Itching, Foreign Body Sensation, Blurred Vision, Eye Dryness, Photophobia, and Pain
- Ocular Surface Disease Index

13.3.1 FLUORESCEIN STAINING (ORA CALIBRA® SCALE)

Fluorescein staining will be conducted at all visits at pre-CAE® and post-CAE®. Grading will be conducted using the Ora Calibra® Scale from 0 to 4 with the use of half grade (0.5) increments, where grade 0 = None and 4 = Severe. The regions to be assessed will be the central, superior, inferior, temporal, corneal sum (central, superior, and inferior regions), conjunctival sum (temporal and nasal regions), and total eye score for study eye only.

Visit-based data will be summarized using continuous descriptive statistics for each region, sum score, and time point (pre-CAE®, post-CAE®, and change from pre- to post-CAE®). Change from baseline will also be summarized using continuous descriptive statistics.

Two-sample t-tests will be used to analyze differences between treatment groups at each visit between active treatment and vehicle. The differences in means, two-sided 95% CIs for the difference in means, and two-sided p-values will be reported.

Change from baseline will be analyzed using ANCOVA with adjustment for baseline fluorescein staining score and site, and treatment group as the explanatory variable. The LS means, LS mean differences, SEs, two-sided 95% CIs for LS means, two-sided 95% CIs for the difference in means, and two-sided p-values will be reported from the ANCOVA model. Two-sample t-tests will be used as sensitivity analysis. Paired t-tests will be used to analyze change from baseline within each treatment group.

Analyses will use ITT population with control-based pattern mixture model imputation as described in section 13.1.1. The random number seeds for the monotone imputation and pattern mixture model imputation will be SEED = 879921 and SEED = 562265, respectively.

A subject level listing of fluorescein staining will also be produced.

13.3.2 LISSAMINE GREEN STAINING (ORA CALIBRA® SCALE)

Subjects will undergo lissamine green staining at all visits at pre-CAE® and post-CAE®. The grading in the inferior, superior, central, temporal, nasal, corneal sum (central, superior, and inferior regions), conjunctival sum (temporal and nasal regions), and total eye sum regions will be measured by the Ora Calibra® Corneal and Conjunctival Staining Scale for lissamine green staining. A standardized grading system of 0 to 4 is used for each of the 5 regions with 0 = No Staining and 4 = Confluent Staining. Half (0.5) grade increments may be used. Analyses will be provided for study eye only.

Visit-based data will be summarized using continuous descriptive statistics by treatment group for each region, sum score, and timepoint (pre-CAE®, post-CAE®, and change from pre- to post-CAE®). Change from baseline will also be summarized with continuous descriptive statistics.

Two-sample t-tests will be used to analyze differences between treatment groups at each visit between active treatment and vehicle. The differences in means, two-sided 95% CIs for the difference in means, and two-sided p-values will be reported.

Change from baseline will be analyzed using ANCOVA adjusted for baseline lissamine green staining score and site, and treatment group as the explanatory variable. The LS means, LS mean differences, SEs, two-sided 95% CIs for LS means, two-sided 95% CIs for the difference in means, and two-sided p-values will be reported from the ANCOVA model. Two-sample t-tests will be used as sensitivity analysis. Paired t-tests will be used to analyze change from baseline within each treatment group.

Analyses will use ITT population with control-based pattern mixture model imputation as described in section 13.1.1. The random number seeds for the monotone imputation and pattern mixture model imputation will be SEED = 965464 and SEED = 331546, respectively.

A subject level listing of lissamine green staining will also be produced.

13.3.3 CONJUNCTIVAL REDNESS

The Ora Calibra® Conjunctival Redness Scale for Dry Eye will be performed at all visits at pre-CAE® and post-CAE®. The conjunctival redness scale ranges from 0 to 4 (half increments may be used) where 0 = Normal, without Vasodilation; 1 = Trace Ciliary or Conjunctival Vasodilation; 2 = Broad Ciliary Vasodilation, 3 = Broad Ciliary and Slight, Horizontal Conjunctival Vasodilation; and 4 = Broad Ciliary and Prominent, Horizontal Conjunctival Vasodilation. Analyses will be provided for study eye only.

Visit-based data will be summarized using continuous descriptive statistics by treatment group for each time point (pre-CAE®, post-CAE®, and change from pre-CAE® to post-CAE®). Change from baseline will also be summarized with continuous descriptive statistics.

Two-sample t-tests will be used to analyze differences between treatment groups at each visit between active treatment and vehicle. The differences in means, two-sided 95% CIs for the difference in means, and two-sided p-values will be reported.

Change from baseline will be analyzed using ANCOVA adjusted for baseline redness score and site, and treatment group as the explanatory variable. The LS means, LS mean differences, SEs, two-sided 95% CIs for LS means, two-sided 95% CIs for the difference in means, and two-sided p-values will be reported from the ANCOVA model. Two-sample t-tests will be used as sensitivity analysis. Paired t-tests will be used to analyze change from baseline within each treatment group.

Analyses will use ITT population with control-based pattern mixture model imputation as described in section 13.1.1. The random number seeds for the monotone imputation and pattern mixture model imputation will be SEED = 465526 and SEED = 579516, respectively.

A subject level listing of conjunctival redness will also be produced.

13.3.4 TEAR FILM BREAK-UP TIME

The TFBUT will be recorded at all visits at pre-CAE® and post-CAE®. For each eye, 2 measurements will be taken and averaged unless the 2 measurements are >2 seconds apart and are each <10 seconds, in which case, a third measurement would be taken and the 2 closest of the 3 would be averaged. This average will then be used for analyses. Analyses will be provided for study eye only.

Visit-based data will be summarized using continuous descriptive statistics by treatment group at each time point (pre-CAE®, post-CAE®, change from pre- to post-CAE®). Change from baseline will also be summarized with continuous descriptive statistics at each post-baseline visit.

Two-sample t-tests will be used to analyze differences between treatment groups at each visit between active treatment and vehicle. The differences in means, two-sided 95% CIs for the difference in means, and two-sided p-values will be reported.

Change from baseline will be analyzed using ANCOVA adjusted for baseline TFBUT and site, and treatment group as the explanatory variable. The LS means, LS mean differences, SEs, two-sided 95% CIs for LS means, two-sided 95% CIs for the difference in means, and two-sided p-values will be reported from the ANCOVA model. Two-sample t-tests will be used as sensitivity analysis. Paired t-tests will be used to analyze change from baseline within each treatment group.

Analyses will use ITT population with control-based pattern mixture model imputation as described in section 13.1.1. The random number seeds for the monotone imputation and pattern mixture model imputation will be SEED = 897985 and SEED = 381325, respectively.

A subject level listing of TFBUT will also be produced.

13.3.5 TEAR OSMOLARITY

Tear osmolarity will be measured at Visit 2 (Day 1), Visit 3 (Day 8), Visit 4 (Day 15), and Visit 5 (Day 29) at pre-CAE®. Tear osmolarity will be taken once from the temporal canthus of each eye and the measurement will be recorded. A second reading may be taken if the first reading is out of range. A maximum of 2 attempts

will be made per eye. Tear osmolarity will be measured in milliosmoles per liter (mOsm/L). Analyses will be provided for study eye only.

Visit-based data will be summarized using continuous descriptive statistics by treatment group. Change from baseline will also be summarized with continuous descriptive statistics at each post-baseline visit.

Two-sample t-tests will be used to analyze differences between treatment groups at each visit between active treatment and vehicle. The differences in means, two-sided 95% CIs for the difference in means, and two-sided p-values will be reported.

Change from baseline will be analyzed using ANCOVA adjusted for baseline tear osmolarity and site, and treatment group as the explanatory variable. The LS means, LS mean differences, SEs, two-sided 95% CIs for LS means, two-sided 95% CIs for the difference in means, and two-sided p-values will be reported from the ANCOVA model. Two-sample t-tests will be used as sensitivity analysis. Paired t-tests will be used to analyze change from baseline within each treatment group.

Analyses will use ITT population with control-based pattern mixture model imputation as described in section 13.1.1. The random number seeds for the monotone imputation and pattern mixture model imputation will be SEED = 542354 and SEED = 8976544, respectively.

A subject level listing of tear osmolarity will also be produced.

13.3.6 UNANESTHETIZED SCHIRMER'S TEST

Unanesthetized Schirmer's test will be conducted at all visits at pre-CAE®. The Schirmer's test strip will be placed in the lower temporal lid margin of each eye. After 5 minutes, the test strip will be removed and the length of the moistened area will be recorded in mm for each eye. Lower values indicate less tears produced in the eye. Analyses will only be produced for study eye.

Visit-based data will be summarized using continuous descriptive statistics by treatment group. Change from baseline will also be summarized with continuous descriptive statistics.

Two-sample t-tests will be used to analyze differences between treatment groups at each visit between active treatment and vehicle. The differences in means, two-sided 95% CIs for the difference in means, and two-sided p-values will be reported.

Change from baseline will be analyzed using an ANCOVA model with adjustment for baseline unanesthetized Schirmer's test reading and site, and treatment group as the explanatory variable. The LS means, LS mean differences, SEs, two-sided 95% CIs for LS means, two-sided 95% CIs for the difference in means, and two-sided p-values will be reported from the ANCOVA model. Two-sample t-tests will be used as sensitivity analysis. The mean differences, SEs, two-sided 95% CIs for the difference in means, and two-sided p-values will be reported from the sensitivity analyses where applicable. Paired t-tests will be used to analyze change from baseline within each treatment group.

Analyses will use ITT population with control-based pattern mixture model imputation as described in section 13.1.1. The random number seeds for the monotone imputation and pattern mixture model imputation will be SEED = 6342576 and SEED = 765121, respectively.

A subject level listing of unanesthetized Schirmer's test will also be produced.

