For the primary analysis, the primary efficacy endpoint of inferior corneal fluorescein staining will have missing data imputed using a control-based pattern mixture model under the assumption of a missing not at random mechanism. The imputation will first impute non-monotone missing data using MCMC to obtain a dataset with a monotone missing pattern, then a control-based pattern mixture model will be run. The SAS® code for obtaining multiple pattern mixture model imputation data is:

```

PROC MI DATA = INDATA SEED = 6849548 OUT = MDATA NIMPUTE = 100
      MINIMUM = 0 MAXIMUM = 4 ROUND = 0.5;
      BY TREATMENT;
      MCMC IMPUTE=MONOTONE;
      VAR BASELINE IFS4 IFS5;
      RUN;
  
```

```

PROC MI DATA = MDATA SEED = 3541655 OUT = OUTDATA NIMPUTE = 1
  
```

```

        MINIMUM = . 0 0 0 MAXIMUM = . 4 4 4 ROUND = . 0.5 0.5 0.5;
        BY _Imputation_;
        CLASS TREATMENT;

        MONOTONE REG(IF54 = BASELINE/ DETAILS);
        MONOTONE REG(IF55 = BASELINE IF54/ DETAILS);
        MNAR MODEL(IF54 IF55 / MODELOBS=(TREATMENT='Vehicle'));
        VAR BASELINE IF54 IF55;
RUN;

```

where

- *INDATA* is the name of the input dataset
- *MDATA* is the name an intermediary dataset with a monotone missing pattern
- *OUTDATA* is the name of the output dataset
- *TREATMENT* is the name of the treatment group variable
- *BASELINE* is the baseline inferior corneal fluorescein staining
- *IF54-IF55* are the inferior corneal fluorescein staining at Visits 4 (Day 15) through Visit 5 (Day 29)

If multiple pattern mixture model imputation fails to generate imputations, baseline total sum fluorescein staining score will be added to the `VAR` statement and multiple imputation will be reattempted. If multiple imputation still fails to generate the required imputation, then `MINIMUM`, `MAXIMUM`, and `ROUND` statements will be removed.

After the imputed data sets are obtained, the following code will be used to execute the ANCOVA model on each imputed data set and the results combined from the analyses:

```

PROC MIXED DATA = OUTDATA;
    BY _IMPUTATION_;
    CLASS TREATMENT SITE;
    MODEL CHG = BASELINE TREATMENT SITE/ SOLUTION COVB;
    LSMEANS TREATMENT / CL PDIFF;
    ODS OUTPUT LSMEANS = OUTLS DIFFS = OUTDIFFS;
RUN;

PROC SORT DATA=OUTLS; BY TREATMENT _IMPUTATION_; RUN;
PROC MIANALYZE DATA=OUTLS;
    BY TREATMENT;
    MODELEFFECTS ESTIMATE;
    STDERR STDERR;
RUN;

DATA OUTDIFFS;
    SET OUTDIFFS;
    COMPARISON = TREATMENT||' - '||LEFT(_TREATMENT);

```

```

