The primary analysis will use control-based pattern mixture model imputation on the ITT population at Visit 5 (Day 29). SAS® code for the multiple imputation analysis will resemble the code in Section 13.1.1 for inferior corneal fluorescein staining. The random number seeds for the monotone imputation and pattern mixture model imputation described in Section 13.1.1 will be SEED = 354846 and SEED = 956546, respectively. In addition, the rounding parameter will be ROUND = 1.

Should control-based pattern mixture model imputation fail to produce the required imputations, baseline measurements of overall ocular discomfort, burning, dryness, grittiness, and stinging from the Ora Calibra® Ocular Discomfort & 4-Symptom Questionnaire will be added to the VAR statement in an iterative fashion until imputation is successful. If multiple imputation still fail to generate the required imputations, then MINIMUM, MAXIMUM, and ROUND statements will be removed.

Sensitivity analyses will be performed using on the ITT population using observed data only and ITT population using LOCF.

Sensitivity analyses under the assumption of a missing at random mechanism will be performed using MCMC imputation on the ITT population as described in section 13.1.1 except the random number seed for PROC MI will be SEED = 146645 and the rounding parameter will be ROUND = 1.

Should MCMC imputation fail to produce the required imputations, baseline measurements of overall ocular discomfort, burning, dryness, grittiness, and stinging from the Ora Calibra® Ocular Discomfort & 4-Symptom Questionnaire will be added to the VAR statement in an iterative fashion until imputation is successful. If MCMC multiple imputation still fail to generate the required imputation, then MINIMUM, MAXIMUM, and ROUND statements will be removed.

Tipping point analysis will be included for further sensitivity analyses in the manner described in section 13.1.1. Then, the monotone datasets will be imputed using a set of shift values for the active treatment group. The random number seeds for the monotone imputation and pattern mixture model imputation described in Section 13.1.1 will be SEED = 5324652 and SEED = 236135, respectively. The set of shift values for the imputation will be from 0 to 4.0 by 0.1 increments. The MINIMUM, MAXIMUM, and ROUND statements will be removed.

Further, primary efficacy analyses will be performed with the PP population with observed data only for sensitivity analysis.

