13.2 Important Secondary Analyses

13.2.1 UNANESTHETIZED SCHIRMER'S TEST AT VISIT 5 (DAY 29), [REDACTED] K-161 [REDACTED] vs VEHICLE [REDACTED]

Unanesthetized Schirmer's test will be conducted at all visits at pre-CAE®. The Schirmer's test strip will be placed in the lower temporal lid margin of each eye. After 5 minutes, the test strip will be removed and the length of the moistened area will be recorded in mm for each eye. Lower values indicate less tears produced in the eye. Analyses will only be produced for study eye.

Unanesthetized Schirmer's test will be summarized at Visit 5 (Day 29) Pre-CAE® by treatment groups using continuous descriptive statistics. Primary analysis will use an ANCOVA model adjusted for baseline unanesthetized Schirmer's test, site and with treatment group as the explanatory variable. Changes from baseline for each treatment group in ocular discomfort will be compared between [REDACTED] K-161 [REDACTED] and vehicle [REDACTED]. In addition, treatment by baseline and treatment by study site interactions will be explored in separate models to evaluate how the treatment effect may differ for baseline value and study sites. In the case of a significant interaction at the 0.05 level, analyses will be performed by baseline median stratification and/or site to understand how the treatment effect differs for baseline value and study sites. Least squares means for each treatment group and the LS mean difference between treatment groups will be presented from the models together with SE, two-sided p-values, and two-sided 95% CIs.

The primary analysis will use control-based pattern mixture model imputation with the ITT population. The random number seeds for the monotone imputation and pattern mixture model imputation described in Section 13.1.1 will be SEED = 465485 and SEED = 849159, respectively. The MINIMUM, MAXIMUM, and ROUND statements will be removed.

Sensitivity analyses will be performed using on the ITT population using observed data only and ITT population using LOCF.

Sensitivity analyses under the assumption of a missing at random mechanism will be performed using MCMC imputation on the ITT population as described in section 13.1.1 except the random number seed for PROC MI will be SEED = 884564 and the MINIMUM, MAXIMUM, and ROUND statements will be removed.

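### Imputation code in SAP 13.3 carries 0–4 limits onto endpoints with other scales, and tipping-point step 2 imputes all arms from one pooled regression

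*SAP*

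**What the plan says.** **Limits and rounding.** The primary staining imputation (SAP 13.1.1) has two steps. Step 1 sets "MINIMUM = 0 MAXIMUM = 4 ROUND = 0.5"; step 2 sets "MINIMUM = . 0 0 0 MAXIMUM = . 4 4 4 ROUND = . 0.5 0.5 0.5". If imputation fails, a baseline staining score is added to the variable list first. The limits go only after a second failure: "If multiple imputation still fails to generate the required imputation".

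**Stated exceptions.** For ocular discomfort (ODS), SAP 13.1.2 changes the rounding: "In addition, the rounding parameter will be ROUND = 1". For Schirmer's (13.2.1) and TFBUT (13.2.2) as important secondary endpoints: "The MINIMUM, MAXIMUM, and ROUND statements will be removed".

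**Section 13.3.** Subsections 13.3.1 to 13.3.8, 13.3.8.1 and 13.3.9 to 13.3.11, twelve in all, refer back to 13.1.1: "Analyses will use ITT population with control-based pattern mixture model imputation as described in section 13.1.1". Each then gives new seeds and nothing else. For secondary TFBUT, for example: "The random number seeds for the monotone imputation and pattern mixture model imputation will be SEED = 897985 and SEED = 381325, respectively".

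**Tipping point.** In the 13.1.1 code, step 1 runs by treatment. Step 2 runs by imputation number only. TREATMENT appears in its CLASS statement and in the `MNAR ADJUST` statement, but not in the regression equations or the VAR list. Sections 13.1.2, 13.2.1 and 13.2.2 reuse this code. For ODS the grid runs "from 0 to 4.0 by 0.1 increments. The MINIMUM, MAXIMUM, and ROUND statements will be removed".

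**The concern.** Because the SAP names an exception wherever it wants one, silence in 13.3 reads as keeping the 0–4 limits. Day 29 Schirmer's and post-CAE TFBUT would then be reported twice, once imputed without limits (13.2) and once with them (13.3). Truncated imputation need not fail, so the fallback may never act and nothing in the output would show the error.

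The tipping-point analysis has one main result: the shift at which significance is lost. That shift means something only if shift 0 is a defined starting model. As coded, K-161 data inform the vehicle imputations and vehicle data inform the K-161 imputations. Shift 0 therefore matches neither the by-arm missing-at-random analysis nor the vehicle-based primary analysis, both set out in 13.1.1.

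**Working it through.** **Plan's own figure (SAP 5, ODS).** SD 0.82, difference 0.49, 60 per arm. SE = 0.82 × √(2/60) = 0.150. Power = Φ(0.49/0.150 − 1.96) = 90.5% (90.1% with the t distribution). The stated 90% is reproduced, and these inputs are used below. The documents give no missing rates, no correlations, and no distributions for Schirmer's, TFBUT or the questionnaire; all of these are assumed.

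**(a) Scales against limits of 0–4**

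| 13.3 endpoint | Scale in the SAP | Do the limits fit? |
|---|---|---|
| Regional staining, redness | 0–4, half grades | yes |
| Staining sums | three regions 0–12, two 0–8, five 0–20 | no |
| TFBUT | seconds | no |
| Schirmer's | mm | no |
| Osmolarity | mOsm/L | no |
| Blink rate | blinks per 60 s | no |
| Questionnaire | 0–5 | no; a 5 cannot be imputed |
| VAS, OSDI | 0–100 | no |
| ODS (13.3.8, 13.3.8.1) | 0–4, whole grades | limits yes, rounding no |

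*Error per truncated value.* For a normal draw with mean μ and SD σ, kept only inside [0, 4], with a = (0−μ)/σ and b = (4−μ)/σ:

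mean = μ + σ[φ(a) − φ(b)]/[Φ(b) − Φ(a)]; acceptance = Φ(b) − Φ(a).

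- TFBUT, μ 2.5–4, σ 1–2: error −0.12 to −1.45 s. At μ 4, σ 1.5 the mean is 2.83 and acceptance 50%.
- Schirmer's, μ 4–8, σ 3–5: error −1.7 to −5.7 mm. At μ 5, σ 4 the mean is 2.24 and acceptance 30%.
- Questionnaire, μ 2–3.5, σ 1–1.4, compared with limits of 0–5: error −0.05 to −0.45.

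*Effect on the analyses.* The error in an arm mean is roughly missing fraction × error per value. At 10% missing:

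- TFBUT: −0.01 to −0.15 s
- Schirmer's: −0.17 to −0.57 mm
- questionnaire: −0.005 to −0.045

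Between arms the error is roughly the difference in missing fractions × error per value. It is near zero at equal missingness. At 10% against 5% for Schirmer's it is 0.05 × (−1.7 to −5.7) = −0.09 to −0.28 mm.

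*Does the fallback help?* This was simulated with 5–10% of 240 subjects missing, 100 imputations and an assumed redraw limit. The chance that at least one value cannot be imputed is:

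- questionnaire: 0%
- TFBUT: 0–55% at 100 redraws, at most 12% at 1,000
- Schirmer's: 7–99% at 100 redraws, 1–65% at 1,000

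The questionnaire would therefore be truncated silently, and TFBUT usually so. For Schirmer's the data would decide. Osmolarity near 300 mOsm/L has essentially zero acceptance, so there the fallback would act.

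*ODS rounding.* About half of imputed values would be half grades, moving the mean by under 0.02.

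**(b) Tipping point at shift 0**

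`MNAR ADJUST` selects whose values are shifted. Unlike the `MODELOBS` option in the primary code, it does not restrict which subjects fit the regression.

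Let d be the primary-arm effect, m_A and m_V the missing fractions in that arm and in vehicle, and p the mean effect over all observed subjects (vehicle counted as 0). With Visits 4 and 5 both missing and no limits:

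estimate = d(1 − m_A) + m_A·p − m_V·p.

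By-arm imputation gives d. At equal missingness m, the pooled code gives d(1 − m).

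- ODS, 10% missing: 0.9 × (−0.49) = −0.441. Simulation gives −0.44 with both visits missing and about −0.45 with Visit 4 observed, against −0.48 to −0.49 by arm. Overall: about −0.44 to −0.46.
- Staining, 10% missing, limits ignored: 0.9 × (−0.46) = −0.414.

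*ODS tipping shift*, unadjusted, with 1.96 × 0.150 = 0.293:

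- by arm: (0.49 − 0.293)/0.10 = 1.97
- pooled: (0.441 − 0.293)/0.10 = 1.48, or (0.46 − 0.293)/0.10 = 1.67

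Simulated medians (300 trials per scenario) are 1.5–1.8 pooled against 1.9–2.0 by arm.

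*Unequal missingness with four arms.* Take 20% missing in the primary arm, 5% in vehicle and 10% in the other two, which leaves 48, 57, 54 and 54 observed (213).

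- d = 0, other arms −0.5: p = −0.5 × 108/213 = −0.254; estimate = 0.15 × (−0.254) = −0.038, against 0 by arm.
- d = −0.2, other arms −0.6: p = (−0.2 × 48 − 0.6 × 108)/213 = −0.349; estimate = −0.160 + 0.15 × (−0.349) = −0.212, against −0.200 by arm.

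**(c) List lengths.** Step 2 of both the primary and the tipping-point code gives four entries for each of the minimum, maximum and rounding options, but VAR names three variables. The leading missing entry is consistent with TREATMENT having been dropped from VAR. IFS4 and IFS5 receive 0–4 on either reading, so no numerical effect is claimed.

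**The case against.** The 13.1.1 code names inferior-staining variables and must be adapted for every endpoint anyway, and 13.1.2 says only that the ODS code will resemble it. Limits of 0–4 are visibly absurd for osmolarity. The removals in 13.2.1 and 13.2.2 show that the authors knew the limits do not suit Schirmer's and TFBUT, so 13.3 may simply lack a repeated sentence. That may well be the intention. But the written rule is the opposite, and settling it while programming after unmasking would be a post hoc choice.

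The stakes are also modest. SAP 8.5 makes the 13.3 analyses exploratory, between-arm error is near zero at equal missingness, and the tipping point is one of several sensitivity analyses. All of that stands and keeps the severity low.

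Three stronger readings are tempting, and the documents do not support them:

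- *The pooled regression is always conservative and harmless when there is no effect.* The design has four arms and optimum dosage is an objective, so equal effects across K-161 arms cannot be assumed. The two unequal-missingness cases above are counterexamples.
- *The tipping shift is too small for all four hierarchical endpoints.* It was computed for ODS only. For staining it depends on how the 0–4 limits act on shifted values; for Schirmer's and TFBUT the documents give no effect size.
- *A single trial-level figure describes the truncation error.* The inputs are assumed, so only ranges are warranted.

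**Conclusion.** Both rules are wrong as written. Neither touches the primary imputation model, the hierarchical tests or the sample size.

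The limits error is certain as a matter of text; its size rests on assumed distributions and missing rates. It falls mainly on arm means and the planned within-arm paired t-tests. It also leaves Day 29 Schirmer's and post-CAE TFBUT open to two conflicting results. For ODS only the rounding is inconsistent, with negligible effect.

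The tipping-point code lacks a defined starting model. The shift-0 difference is attenuated when missingness is equal, or when all K-161 arms have similar effects. It can be non-zero under no primary-arm effect, or anti-conservative, when missingness is unequal and the other K-161 arms do better. The ODS tipping shifts quoted assume 10% missing in each arm and the SAP's SD and difference.

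Severity: a minor to should-fix code correction.

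**What to change.** - 13.3.4 to 13.3.7, 13.3.10 and 13.3.11: state that the minimum, maximum and rounding options are removed, rather than rely on the fallback.
- 13.3.9: remove them or set 0–5.
- 13.3.8 and 13.3.8.1: set rounding to 1, as in 13.1.2.
- 13.3.1 and 13.3.2: impute the regions and add them up, or give limits that fit each sum.
- Tipping-point step 2: add TREATMENT to both the regression equations and the VAR list, or run the step by arm. Changing VAR alone is not enough, because the regression effects are listed explicitly.
- Primary and tipping-point step 2: match the lengths of the minimum, maximum and rounding lists to VAR.

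Cost: a few lines of SAP text and program code, settled before unmasking. No new data are needed.
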